RESEARCH PROTOCOL
Version no 4.0	Clinical intervention study

Clinical study protocol reference number: EC number REK Vest 421917.

Sleeve Pex

A clinical intervention study exploring gastropexy as a measure to reduce gastro-oesophageal reflux disease after laparoscopic sleeve gastrectomy.

Person responsible for research at responsible institution: [name] Entity responsible for research: Helseforsking Sogn og Fjordane, Helse Førde, Norway

Revision history

Version number	Date
1	06.01.2022
2	15.11.2022
3	16.12.2022
4	21.08.2023

[name]		
Project Leader Signature	Date	
[name]		
Representative for the research responsible institution	Date	

Signature

This document contains confidential and proprietary information and may not be copied or reproduced in whole or part without the written permission of [name].

Version no 4.0 RESEARCH PROTOCOL Clinical intervention study

CLINICAL STUDY AGREEMENT SIGNATURE LOG

I, the undersigned, have read and understand the specific research protocol, and agree with the contents.

I agree to conduct in person or to supervise the study.

I agree to ensure that all who assist me in the conduct of the study have access to the research protocol plus any amendments and are aware of their obligations.

Researcher:			
Name	Signature	 Date	_
Institution			

Project Leader Name: [name]

Professional position: MD, PhD Address: [name]

E-mail address: [contact]

[contact]

Contact information of other study sites in which the clinical study will be conducted.

Name: [name]

Professional position: MD, [name]: Uppsala University Hospital

E-mail address: [contact]

[contact]

	RESEARCH PROTOCOL
Version no 4.0	Clinical intervention study

CLINICAL STUDY SUMMARY

Title:	Sleeve-pex.
Study objectives:	Reduce gastro-oesophageal reflux disease (GORD) after laparoscopic sleeve gastrectomy (LSG).
Clinical study design:	Interventional.
	A randomized clinical control trial where patients planned for LSG are randomized to LSG with or without gastropexy.
Inclusion / exclusion criteria:	Inclusion criteria:
	Patients planned for bariatric surgery with primary LSG.
	Exclusion criteria:
	Age below 18 years.
	Use of acid-reducing medication (ARM) for other reasons than reflux.
	Previous antireflux surgery.
	Inability to comprehend and respond to patient related outcome (PRO) questionnaire.
	LSG planned as the first step of Biliopancreatic Diversion with Duodenal Switch (BPDDS).
Primary performance endpoints:	Continuous use of acid-reducing medication (ARM) due to reflux symptoms at two years after surgery, or reoperation due to GORD within two years postoperatively.
Sacandary narformana	Patient reported outcome (HRQL and GerdQ).
Secondary performance endpoints:	Endoscopic findings (visible oesophagitis, hiatal hernia), pH-metry and impedance in a subgroup of patients.
Safety endpoints:	Complications graded as Clavien Dindo grade 3b or worse.
Duration of study:	Eight years.
Follow-up:	Six weeks: Focusing on 30 day complications.
	One, two, and five years: Clinical, biochemical and PRO-data.
	At two years also endoscopy, pH-metry and impedance measurements.

TABLE OF CONTENTS

Clinical atudy care	amant aignatura l	09
Cilnical Sidov adre	emeni sionalure i	()()
ommodi otday agro	onnone orginataro	♥ Ŋ

RESEARCH PROTOCOL

Version no 4.0

Clinical intervention study

Cl	inical stu	udy s	ummary	3
Ta	able of C	Conte	nts	3
Li	st of abb	revia	tions and definition of terms	7
1	Intro	oducti	on	10
2	Stud	dy De	scription	10
	2.1	Bac	kground	10
	2.2	Stuc	ly Rationale	10
3	Obje	ective	s and hypothesis	11
	3.1	Clini	ical study - objectives	11
	3.1.	1	Primary objective	11
	3.1.	2	Secondary objective	11
	3.1.3	3	Other study objectives	11
	3.2	Нур	othesis	11
	3.3	Any	results expected during the project period	11
	3.4	Risk	s and anticipated adverse events that are to be assessed	12
4	Proj	ect m	nethodology	12
5	Stud	dy de	sign	12
	5.1	Gen	eral	12
	5.1.	1	Description	12
	5.1.2	2	Primary and secondary endpoints	12
	5.1.	3	Equipment	13
	5.1.	4	Methodology	14
	5.1.	5	Measures to minimise bias	14
	5.1.0	6	Including more subjects to compensate for drop-outs	14
	5.2	Stuc	ly treatment	15
	5.2.	1	Description	15
	5.2.	2	Justification comparator	15
	5.2.3	3	Concomitant therapy	15
6	Risk	s and	d benefits	15
	6.1		cipated clinical benefits	
	6.2	Anti	cipated adverse events	15
	6.3		sible interactions with concomitant (medical) treatments	
	6.4	Step	os to be taken to control or mitigate risks	15
	6.5	Sub	jects	
	6.5.	1	Inclusion criteria	16

RESEARCH PROTOCOL

Version no 4.0

Clinical intervention study

	6.5.	2 Exclusion criteria	16
	6.5.	3 Criteria for withdrawal or discontinuation	16
	6.5.	4 Enrolment	16
	6.5.	5 Duration clinical study	16
	6.5.	6 Expected subject duration	17
	6.5.	7 Number of subjects	17
	6.5.	8 Time to select all subjects	17
	6.6	Procedures	17
	6.6.	1 Clinical study procedures	17

17.2	Gastroskopi (gastroscopy)	29
17.3	Kontroll av operasjonsteknikk (verification of operation technique)	30
17.4	Bruk av syreblokkerande medisin (use of acid-reducing medication)	31
17.5	Reoperasjon grunna refluks (reoperations for reflux)	32
17.6	Månadsvis oversikt over inkluderte pasientar (monthly overview of included patients)	32

	RESEARCH PROTOCOL
Version no 4.0	Clinical intervention study

LIST OF ABBREVIATIONS AND DEFINITION OF TERMS

Abbreviation or special term	Explanation
AE (Adverse Event)	An unfavorable change in the health of a participant that happens during a clinical. This change may or may not be caused by the intervention being studied.
ARM	Acid-reducing medication
ASMBS	American Society for Metabolic and Bariatric Surgery
BPDDS	Biliopancreatic Diversion with Duodenal Switch
CRF	Case Report Form (electronic or paper)
Clinical study	A research study using human subjects to evaluate biomedical or health-related outcomes. Two types of clinical studies are Interventional studies (or clinical trials) and Observational studies
Completed	The clinical study has ended normally, and participants are no longer being examined or treated (that is, the "last subject, last visit" has occurred).
Controlled trial	A type of clinical trial in which observations made during the trial are compared to a standard, called the control. The control may be observations of a group of participants in the same trial or observations from outside the trial (for example, from an earlier trial, which is called a historical control).
DMC	Data Monitoring Committee
EC	Ethics Committee, synonymous to Institutional Review Board (IRB) and Independent Ethics Committee (IEC) and Regional Ethics Committee (REC)
Eligibility Criteria	The key standards that people who want to participate in a clinical study must meet or the characteristics they must have. Eligibility Criteria include both inclusion criteria and exclusion criteria. For example, a study might only accept participants who are above or below certain ages.
Enrollment	The number of participants in a clinical study. The "estimated enrollment" is the number of participants that the researchers need for the study.
Exclusion criteria	The factors, or reasons, that prevents a person from participating in a clinical study.
GerdQ	Gastro-oesophageal reflux disease questionnaire
GOJ	Gastro-oesophageal junction
GORD	Gastro-oesophageal reflux disease. In this document defined as either daily use of ARM for at least one month due to reflux symptoms, or based on findings on endoscopy, pH-metry or impedance.

	RESEARCH PROTOCOL
Version no 4.0	Clinical intervention study

HRQL	Health related quality of life
IFSO	International Federation for Surgery of Obesity
Inclusion criteria	The factors, or reasons, that allows a person to participate in a clinical study.
Intervention Model (Design)	The general design of the strategy for assigning interventions to participants in a clinical study.
Interventional study (or clinical trial)	A clinical study in which participants are assigned to receive one or more interventions (or no intervention) so that researchers can evaluate the effects of the interventions on biomedical or health-related outcomes. The assignments are determined by the research protocol. Participants may receive diagnostic, therapeutic, or other types of interventions
ITT	Intention to treat analysis.
LOS	Lower Oesophageal Sphincter
LSG	Laparoscopic sleeve gastrectomy
LSGG	Laparoscopic sleeve gastrectomy with gastropexy. Gastropexy in this document means suturing the staple-line of the gastric remnant to the gastrocolic ligament including the gastroepiploic arterial arcade.
Primary Outcome Measure	The planned Outcome Measure in the protocol that is the most important for evaluating the effect of an intervention. Most clinical studies have one Primary Outcome Measure, but some may have more than one.
Primary Purpose	The main reason for the clinical trial. The types of Primary Purposes are Treatment, Prevention, Diagnostic, Supportive Care, Screening, Health Services Research, Basic Science, and Other.
Principal Investigator	Statistician working in SOReg-Norway
PRO	Patient Reported Outcome
Protocol	The written description of a clinical study. It includes the study's objectives, design, and methods. It may also include relevant scientific background and statistical information.
Secondary Outcome Measure	A planned Outcome Measure in the protocol that is not as important as the Primary Outcome Measure but is still of interest in evaluating the effect of an intervention. Most clinical studies have more than one Secondary Outcome Measure.
Serious Adverse Event (SAE)	An adverse event that results in death, is life- threatening, requires inpatient hospitalization or extends a current hospital stay, results in an ongoing or significant incapacity or interferes substantially with normal life functions. Medical events that do not result

	RESEARCH PROTOCOL
Version no 4.0	Clinical intervention study

	I
	in death, are not life-threatening, or do not require hospitalization may be considered serious adverse events if they put the participant in danger or require medical or surgical intervention to prevent one of the results listed above.
	By definition, any complication classified as Clavien Dindo grade 3b or more is a serious adverse event.
SOReg	Scandinavian Obesity Surgery Register. Consists of SOReg Sweden (SOReg-S) and SOReg Norway (SOReg-N).
Study completion date	The date on which the final data for a clinical study were collected because the last study participant made the final visit to the study location (that is, "last subject, last visit"). The "estimated study completion date" is the date that the researchers assume will be the completion date for the study.
Study start date	The date on which the enrollment of participants for a clinical study began
TSC	Trial Steering Committee

	RESEARCH PROTOCOL
Version no 4.0	Clinical intervention study

1 INTRODUCTION

LSG has become the most commonly performed bariatric procedure worldwide.¹ The operation consists of a longitudinal resection of the stomach leaving the intestines intact, thereby lowering the risk for side-effects due to rerouting of the small bowel.

Although such side-effects mostly are avoided, GORD has been reported to increase after LSG. Increased intragastric pressure, loss of distensibility, kinks/torsion of the gastric remnant, development of a neo-fundus, dysfunction of the LOS, and intrathoracic migration of the upper part of the remaining stomach have all been postulated as potential mechanisms of the increased incidence of GORD after LSG.²⁻⁴

The LOS has a crucial role in preventing reflux, and the two most important factors for its function are: a) an intra-abdominal position, and b) proximity to the crural diaphragm. Based on this, *[name]* et al sutured the gastric remnant to the gastrocolic ligament (gastropexy) in an attempt to prevent kinks, torsion and intrathoracic migration, and found less use of ARM two years postoperatively in the LSGG-group than in the LSG group.⁵

The proposed study is a multi-centre, randomized, clinical intervention study designed to examine the outcome of LSGG. Since gastropexy is not routinely performed in most centers, the technique represents a challenge to current practice.

900 patients will be enrolled in this study, please see calculation of sample size (chapter 7.2).

2 STUDY DESCRIPTION

2.1 Background

GORD is an obesity-related disease, and in the SOReg-N we find that ≈ 17 % of all patients undergoing bariatric surgery are using acid-reducing medication (ARM) preoperatively. In addition, patients might have asymptomatic reflux. This can be detected by gastroscopy and/or 24hr pH-measuring.

After LSG, many centers report an increase in the use of ARM. In the study by [name] et al, the use of ARM increased from 10% preoperatively to 30% after two years in the group without gastropexy.⁵ In a recent review article including 10 718 patients, the authors found an increase of 19% from preoperative until two years or more after the operation, and de novo reflux (i.e. new reflux) of 20% but with large variations between institutions.⁶

2.2 Study Rationale

The intention is to refine the LSG in order to prevent/reduce an increase in the prevalence of GORD after this operation.

Symptoms of reflux can be anything from mild dyspepsia to severe, nightly reflux/regurgitation affecting sleep. Reflux can also be asymptomatic. Independent of whether it is symptomatic or not, it can induce oesophagitis and possibly Barret's. Because of this, both the ASMBS and IFSO recommends pre- and postoperative gastroscopy for sleeve-operated patients as surveillance.^{7, 8} Although many patients will experience reduced symptoms when starting ARM, symptom control is not achieved in all. Also, oesophagitis might not heal even when using high doses of ARM. In such cases revisional surgery might be necessary to alleviate the reflux.

For the individual, avoiding GORD will improve HRQL and reduce the need for ARM and revisional surgery due to reflux issues.

	RESEARCH PROTOCOL
Version no 4.0	Clinical intervention study

The cost of adding gastropexy to the LSG is considered minimal as it requires almost no equipment costs, and only requires a longer operation time in the range of 10 - 15 minutes.

For the society and public health service, avoiding reflux will reduce healthcare expenditure due to reduced need for medical consultations, ARM, revisional surgery and surveillance. Considering the high number of LSG being performed worldwide, the potential for reduced costs is large.

Academically, this study might give new insight into the mechanism(s) for reflux after LSG.

3 OBJECTIVES AND HYPOTHESIS

3.1 Clinical study - objectives

3.1.1 Primary objective:

Reduce GORD after LSG as evaluated by the use of ARM and reoperations due to GORD.

3.1.2 Secondary objectives:

- a) Evaluate PRO using the GerdQ and guestions on HRQL.
- b) Prevent ascend of the GOJ as evaluated by endoscopy.
- c) Reduce GORD as evaluated by endoscopy and pH-metry.

3.1.3 Other study objectives

None as planned per today.

3.2 Hypothesis

Kinks and torsion of the gastric remnant may obstruct the passage of food and fluid through the gastric remnant thereby predisposing to reflux. It has also been found that the GOJ ascends following LSG, thereby leading to the formation of a gastric pouch (hiatal hernia) above the diaphragm.⁴ There is a clear association between hiatal hernia and reflux, and an ascend of the gastric remnant could therefore be the main reason for development of reflux after LSG.^{9, 10}

The hypothesis is that suturing the gastrocolic ligament (including the gastroepiploic artery) to the remnant stomach will prevent kinks, torsion and intrathoracic migration of the gastric remnant and hence reduce the incidence of GORD.

3.3 Any results expected during the project period

Safety will be monitored continuously. The inclusion period is estimated to approximately two years, and the follow-up for primary and secondary objectives will be two and five years postoperatively. Adding 6-12 months to collect and clean the data gives a project period of eight years. It is expected that both primary and secondary objectives for the two year outcome will be achieved 6-7 years after commencement of the study.

RESEARCH PROTOCOL Version no 4.0 Clinical intervention study

Figure 1. Time-schedule of the project.

3.4 Risks and anticipated adverse events that are to be assessed

Leaks from the stomach remnant and bleeding from the stomach or gastrocolic ligament are well-known adverse events following LSG that will be assessed. However, none of these have been found to increase after LSGG in previous studies. Unintentional kinking / torsion / stricture of the gastric remnant could be potential adverse events of the gastropexy, but our hypothesis is that these will be reduced or prevented by this technique.

Prolonged operation time is foreseeable and could possibly lead to unanticipated adverse events. If so, this should become evident in the 30 day morbidity report and presented to the DMC.

4 PROJECT METHODOLOGY

Hospitals performing more than 10 LSG annually will be invited to participate. A maximum of 200 patients will be accepted from any hospital. The start of the study is the date at which the first patient is operated. The inclusion of new patients will stop when 900 patients have been included (i.e. randomized), estimated to be reached after approximately two years. The number of included patients will be monitored continuously.

Evaluation of outcome will be based on data at two and five years postoperatively. Given an inclusion period of maximum two years, follow-up after two and five years, and another year for delayed follow-up and data processing, the project period will be for a maximum of eight years.

This study is an international, multicentre, randomized, triple-blind (blinded to patients, caregivers and researchers) prospective clinical intervention trial. For primary and secondary endpoints, analysis will be performed according to ITT. All patients will thus be analysed within the allocated group.

5 STUDY DESIGN

5.1 General

5.1.1 Description

This study is a multicentre, randomized, triple-blind, prospective clinical intervention study comparing LSG to LSGG.

5.1.2 Primary and secondary endpoints

The primary endpoint is continuous use of ARM for GORD symptoms, or reoperation due to GORD within two years. This is easily measured and registered in most bariatric surgical

	RESEARCH PROTOCOL
Version no 4.0	Clinical intervention study

registries including SOReg. Daily use of ARM due to dyspepsia during the last month (as defined in SOReg) / reoperation due to GORD will be defined as "yes", otherwise "no".

Secondary endpoints are:

- a) PRO using the GerdQ and questionnaires for HRQL. GerdQ is a six item, easy to use questionnaire developed as a diagnostic tool for GORD.¹¹ It uses a four graded Likert scale (0-3), giving a total GerdQ score range of 0-18. Besides GerdQ, the questionnaires used for evaluating HRQL will be those that are already incorporated in the hospitals that will participate in the study. In Sweden this will be the SF-36, while in Norway only the initial question from SF-36 will be used together with PROSURG.¹²
- b) GORD as evaluated by endoscopy, pH-metry and impedance.

Endoscopy: Thirty patients will be submitted to a gastroscopy prior to, and two years after LSG/LSGG. A standard formula for evaluating and describing findings at gastroscopy will be used (appendix 1).

Reflux oesophagitis will be defined according to the Los Angeles classification (LA grade A-D), where grade C and D entails high-grade oesophagitis. ¹³ LA grade C and D, Barret's oesophagus and a peptic stricture will be considered confirmatory evidence of GORD.

pH-metry: GORD will be defined according to the oesophageal acid exposure time and the number of reflux episodes per 24 hrs. ¹⁴ pH-metry will only be performed in the subgroup of 30 patients before and two years after surgery using the Bravo-capsule. Patients having reflux symptoms responding to PPI but without acid reflux as evaluated by the Bravo capsule will be offered pH-impedance measurement.

c) Presence of a hiatal hernia as evaluated by endoscopy. The distance between the teeth and diaphragm, secondly the teeth and the GOJ will be measured and the difference calculated. If a part of the remaining stomach ascends into the thorax this will predispose to reflux as it is well known that a hiatal hernia (defined as ≥2 cm difference) is a predictor of reflux.¹⁵

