Each participating hospital will point out one person to coordinate the study within that hospital. This includes patient recruitment, obtaining written informed consent, local data management, correspondence with the national coordinator and with the Project Leader / institution responsible for this study. All included patients will be given a unique patient ID number. This number is the ID that is generated automatically by SOReg. All included patients in Sweden will thus have a six digits code number and all included patients in Norway will have a five digits code number. An updated list of included patients with overview of group allocation must be kept in a safe place within the hospital. A copy of this list containing the patient ID (no name or other identifiable data) shall be sent to SOReg-N on the first day of every month (see also 5.1.5 and 5.1.6 and appendix 17.6). Hospitals participating in the Bravo-arm of the study must balance the number of patients themselves so that an equal number of patients are allocated to the pexy and no-pexy group, respectively.

6.6.3 Factors that may compromise the outcome of the clinical study / interpretation of the results

This study is a randomized trial where the patients will be randomized into two groups. Potential differences between the groups like age, preoperative use of ARM and smoking will be accounted for by statistical methods.

Potential differences in performance between surgeons will be explored and adjusted for by statistical methods if found.

Missing values at two years will be accounted for by multiple imputation as necessary. Missing value at baseline will exclude the patient from the study.

Potential differences in culture and tradition between hospitals and countries for prescribing ARM, and similarly potential differences among patients demand for having ARM will be sought overcome by standardizing the information: ARM used in conjunction with the operation should be stopped at the latest by four weeks postoperatively. Patients using ARM after this period should actively be asked about this at the first follow-up (usually six weeks), and if no obvious reason exists it should be stopped. Similarly, if a patient is using ARM at the one-, two- or five year follow-up, the reason for this should be addressed.

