When starting, look for oesophagitis or other pathology in the oesophagus. If oesophagitis is observed; classify according to the Los Angeles classification (grade A, B, C, D).

Pass the endoscope to the duodenum. When retracting the scope, take mucosal-samples from the antrum and body of the stomach in order to check for Helicobacter Pylori (HP). Do not take samples if the patient is using PPI; then use fecal test (advised), blood-test or breathing test.

Retroflect the scope in the upper part of the stomach and evaluate the diaphragmatic opening from below. Grade the opening according to Hill's grade (grad I, II, III, IV). Preoperatively this is easily performed, postoperatively this is often not possible after a sleeve gastrectomy.

Measure the distance from the teeth to the diaphragm, secondly the distance from the teeth to the GO-junction.

If an area is suspicious of Barret`s; estimate the longest and broadest area in cm (Prague Circumferential and Maximal extent (CM) criteria). Only mucosal tongues that extends ≥ 1 cm up from the GO-junction and have intestinal metaplasia are defined as Barret`s.

For postoperative endoscopies: Note the configuration of the gastric remnant. Smooth form? Stricture? Torsion? Other findings? (Findings can be noted under "other findings" in the gastroscopy-modul in SOReg).

Findings should be documented by a photo or video. If biopsies are taken, these should be taken at the end of the procedure.

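### Objective 3.1.2 b is to prevent ascent of the GOJ, but its matching endpoint 5.1.2 c is presence of a hernia (≥2 cm), without a time point or use of the preoperative distance

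*Protocol*

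**What the plan says.** - Protocol 3.1.2, secondary objective b: "Prevent ascend of the GOJ as evaluated by endoscopy". Section 3.2 gives the reasoning: gastropexy is meant to stop the gastric remnant from migrating into the chest.
- Protocol 5.1.2, the matching endpoint: "c) Presence of a hiatal hernia as evaluated by endoscopy". The same paragraph fixes the cut: "hiatal hernia (defined as ≥2 cm difference) is a predictor of reflux". The study summary likewise lists only hiatal hernia for this aspect.
- The centimetre value exists. Section 5.1.2 has the distances from the teeth to the diaphragm and to the GOJ recorded: "secondly the teeth and the GOJ will be measured and the difference calculated". Appendix 17.2 repeats it in the standard gastroscopy text: "Measure the distance from the teeth to the diaphragm, secondly the distance from the teeth to the GO-junction".
- Timing and number (5.1.2): "Thirty patients will be submitted to a gastroscopy prior to, and two years after LSG/LSGG". Section 6.6.1 requires the same standardised form on both occasions.
- Section 6.6.2 asks hospitals in the Bravo part to balance their patients "so that an equal number of patients are allocated to the pexy and no-pexy group, respectively".
- Section 7.10 says in general terms that continuous variables will also be analysed with mixed effect models. It does not name this distance.

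**The concern.** The objective is about movement and the endpoint is about a state, so the two can disagree in a single patient. A GOJ that rises from 0 to 1.5 cm has done what the objective seeks to prevent, yet it counts as no hernia. A difference that falls from 3 cm to 2 cm counts as hernia present. Pre-existing hernias can enter the subgroup, because hernia is not an exclusion criterion (6.5.2) and appendix 17.1 asks for crural repair only where possible.

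With so few patients, reducing a centimetre measurement to yes or no is also costly. A null result on hernia presence would say little about whether gastropexy holds the GOJ down, which is one of the mechanisms that the trial proposes.

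**Working it through.** **The plan's own figure.** The protocol has a sample size for the primary endpoint only. With 14% versus 7%, two-sided alpha 5% and power 85%:

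n per arm = [1.960·√(2·0.105·0.895) + 1.036·√(0.14·0.86 + 0.07·0.93)]² / 0.07² = 343 (rounded up)

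The total is 686, and 686/0.8 = 857.5, rounded up to 858. Both figures reproduce, but they say nothing about the hernia endpoint. For that endpoint the protocol gives only n = 30.

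**Inputs from the protocol.** Thirty patients split equally make 15 per arm. The 20% dropout in 7.4 leaves 15 × 0.8 = 12 per arm.

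**Inputs assumed.** The mean, SD and expected arm difference of the distance are not given. Two sets of assumptions were simulated, with 2,000 trials per setting.

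*Set A, 12 per arm.* The preoperative distance is max(N(0.5, 1), 0) cm. The two-year distance is max(preoperative + N(0, SD) + ascent, 0), with ascent in the LSG arm only. The yes/no analysis is Fisher's test on ≥2 cm at two years. The centimetre analysis is a linear regression of the two-year distance on arm and preoperative distance.

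| Ascent | SD of change | Fisher, ≥2 cm | cm, adjusted |
|---|---|---|---|
| 1.0 cm | 0.8 | 14.5% | 79.6% |
| 1.0 cm | 1.0 | 14.6% | 59.3% |
| 1.0 cm | 1.3 | 11.0% | 38.2% |
| 1.5 cm | 0.8 | 47.7% | 98.6% |
| 1.5 cm | 1.0 | 39.2% | 91.7% |
| 1.5 cm | 1.3 | 31.5% | 70.5% |

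Re-runs with other seeds put Fisher at 10-15% for 1 cm of ascent. With no ascent, the adjusted test rejects in 4-6% of trials, so its advantage does not come from false positives.

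*Set A with repair and rounding.* If every baseline hernia ≥2 cm is taken as reduced to 0 at operation and distances are rounded to whole centimetres, 1 cm of ascent gives 15-27% for Fisher and 32-63% for the adjusted distance. Over both variants the ranges are therefore about 10-27% and 32-80%.

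*Set B.* The LSG mean at two years is 2 cm, the SD 1.0-1.5 cm, the arm difference 1.0-1.5 cm, and the correlation between the two occasions 0.3-0.5. With 15 per arm, Fisher has 15-66% power and the adjusted distance 44-99%. With 12 per arm the figures are 14-52% and 37-98%. At a 1 cm difference, SD 1 cm, correlation 0.5 and 15 per arm they are 34% and 84%.

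**Check without simulation.** For a normal variable cut at prevalence p, the large-sample efficiency of the cut relative to the uncut measure is φ(z)²/[p(1−p)]. This is 64% at p = 50%, 58% at 30% and 49% at 20%. Thirty patients analysed by the cut are then worth about 30 × 0.64 = 19 down to 30 × 0.49 = 15 patients analysed in centimetres.

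**Adjusted distance or simple change.** In Set B with 15 per arm, a 1 cm difference, SD 1 cm and correlation 0.3, the adjusted analysis has 79% power and a t-test on change 62%. Adjustment is the better use of the preoperative value.

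**The case against.** Several points against this have weight.

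- A reader might infer that the endpoint rests on a single endoscopy, or that the centimetre data are thrown away. The protocol says neither. Endoscopy is done twice, the difference is calculated, and 7.10 foresees mixed models for continuous variables. What stands is narrower: endpoint c names no time point and no centimetre quantity, so a later centimetre analysis would not be the endpoint that the protocol declares.
- A reader might also call the cut a misclassification or a source of bias. It is neither. At least 2 cm is the protocol's own definition of hernia, and 3.2 links ascent to hernia and hernia to reflux. Pre-existing hernias add noise to a randomised comparison, not bias. The mismatch exists only relative to objective b.
- Crural repair on the same indications in both arms (6.3) limits carry-over of old hernias. It also moves the GOJ, so an individual change mixes repair with gastropexy. This is a good reason not to read change patient by patient.
- The protocol does not name Fisher's test, which is conservative here. Boschloo's exact test on the same yes/no data raises power at 1 cm of ascent to about 19-27%, or about 23-43% with repair and rounding. The gap shrinks but remains.
- This is not the trial's only view of the mechanism, since appendix 17.2 also records torsion, stricture and the shape of the remnant.
- The choice of test could be left to an analysis plan. The choice of endpoint is made in the protocol itself, and that is what does not match the objective.

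**Conclusion.** The point holds as a mismatch between objective and endpoint with a loss of precision, and not as an error that invalidates a result. Objective b asks whether the GOJ ascends, while endpoint c asks whether a hernia is present. The quantity that answers objective b is already collected.

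The direction is firm: the adjusted centimetre distance had more power than the yes/no cut in every scenario. The size is illustrative, because every SD, mean and difference is assumed. At 12 per arm and 1 cm of ascent it is roughly 10-27% against 32-80%, with the gap depending on the treatment of repaired hernias, rounding and the exact test chosen. Even in centimetres several 1 cm scenarios stay underpowered, so the subgroup remains exploratory. The primary endpoint, the sample size of 900 and safety are not affected.

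**What to change.** In 5.1.2 c, name the two-year diaphragm-GOJ distance in cm, compared between arms with adjustment for the preoperative distance, as the endpoint for objective 3.1.2 b. Keep hernia ≥2 cm, stated as at two years, as a supportive summary by arm and by hernia status at baseline. Bring the study summary into line.

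Add that the result is read as the between-arm difference and not as individual change, because crural repair also moves the GOJ. Adjust for the preoperative distance and not for the repair itself: under 5.1.6 and appendix 17.1, randomisation comes before surgery starts and the hiatus may be judged during the operation.

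The cost is a few sentences in the protocol and the matching line in the analysis plan, settled before any unblinded comparison. No new data, visits or procedures are needed, because the standard gastroscopy procedure already requires both distances on both occasions.
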